#### Rapid initiation of BUP/NX Version 1: Nov-15-2018

months. More than 90% of those who remained in treatment at 12 months were opiate-abstinent (Bachhuber, Thompson et al. 2018). Importantly, and in contrast to many other programs in the City, the STEP program has a waiting list of nearly 200 individuals.

The proposed project incorporates the concept of rapid initiation of MAT and consequently, the rapid control of withdrawal symptoms. A mobile team (Nurse Practitioner, Certified Peer Recovery Specialist, and a Case manager) will provide medication, counseling and treatment engagement support for one month. During this time, individuals will be linked to community MAT providers with unused capacity.

We will determine the economic value of the mobile intervention relative to treatment as usual from the perspective of the City of Philadelphia's Department of Public Health. [name], a Health Economist in the HIV Prevention Research Division, Department of Psychiatry, Perelman School of Medicine at the University of Pennsylvania, will lead this portion of study activities with consultations with colleagues at the Center for Health Economics of Treatment Interventions for Substance Use Disorder, HCV, and HIV (CHERISH). The results of this analysis will inform future policy decisions regarding implementation of this novel, mobile strategy for rapid initiation of MAT as a method for engagement in long-term evidence-based treatment. If the intervention in this study shows positive economic value, the City of Philadelphia's Department of Public Health may scale-up the intervention to reach more people throughout the city that may be at risk of opioid overdose. Enhanced interventions may require a greater amount of resources than alternative methods of more basic interventions or the usual standard of care. However, resource-intensive interventions may be justified through the achievement of better outcomes resulting from administering enhanced procedures.

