## 3.7 Study Measures

All interviews will be administered by experienced research assistants trained in the administration of the proposed assessments. Following confirmation of eligibility, the mobile research assistants will complete the baseline assessment (described below). The participant assessments in this research will be sharply focused on the valid and reliable measurement of its primary endpoints i.e. ongoing treatment engagement will be the primary endpoint on which the study is powered. We will also carefully compare the two groups with respect to the rate of continued opioid use and subsequent overdoses. All assessments will be completed by trained research staff (not clinicians) at baseline, and again at 1- and 6-month post-enrollment. We anticipate follow-up rates of 95% and 90% at Month 1 and 6, respectively. We anticipate that the assessments will take approximately 45 minutes to complete.

- Physical history and examination including a blood test to evaluate the liver function.
- Locator Data Collection: A detailed contact sheet (Locator Form) will be completed for all subjects as part
  of the baseline assessment. We will ask participants to provide contact information on themselves and at
  least three additional people with whom they are most likely to stay in contact. We will also ask about other
  places where participants might be able to be contacted in the future. Participants will provide consent for
  research staff to contact individuals whose contact information they provide. Contact information will also
  include e-mail addresses and mobile phone numbers for texting. The locator form will be updated at each
  scheduled assessment visit. In addition, participants will be asked to call or visit the research staff
  whenever they have updates to provide regarding changes in contact information.
- DSM-5 Substance Use Disorder Checklist: This form is a listing of the eleven DSM-5 criteria for substance use disorder. We will screen for opioids, cocaine, and alcohol as each are necessary for confirmation of inclusion and exclusion criteria. A score of 4-6 is considered moderate severity and from 7-11 is considered severe substance use disorder. An opioid use disorder score of 4 or greater will be required for study eligibility. Alcohol use disorder and benzodiazepine scores of 4 or greater will be exclusionary.
- A study specific questionnaire that includes:

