# 3.8.2 Secondary Study Endpoints

- Evaluate the impact on the number of overdose and evaluate the change in substance use and severity of addiction using a repeated measures model to compare the groups on the ASI drug composite score at months 1 and 6.
- Cost evaluation: We will determine the economic value of the mobile intervention relative to treatment as usual from the perspective of the City of Philadelphia's Department of Public Health. [name], a Health Economist in the HIV Prevention Research Division, Department of Psychiatry, Perelman School of Medicine at the University of Pennsylvania, will lead this portion of study activities with consultations with colleagues at the Center for Health Economics of Treatment Interventions for Substance Use Disorder, HCV, and HIV (CHERISH). The results of this analysis will inform future policy decisions regarding implementation of this novel, mobile strategy for rapid initiation of MAT as a method for engagement in long-term evidence-based treatment. If the intervention in this study shows positive economic value, the City of Philadelphia's Department of Public Health may scale-up the intervention to reach more people throughout the city that may be at risk of opioid overdose. Enhanced interventions may require a greater amount of resources than alternative methods of more basic interventions or the usual standard of care. However, resource-intensive interventions may be justified through the achievement of better outcomes resulting from administering enhanced procedures.

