# 5.2 Sample Size and Power Determination

Our power analysis has been based on this primary aim. Our primary hypothesis is that participants who received rapid induction will more likely be engaged in ongoing treatment at 1- and 6-month follow-up than participants who sought treatment at BAC/CRC. We will test this hypothesis at a 5% level of significance. Our principal interest is in the comparison of engagement rates between the mobile intervention and BAC/CRC groups, at months 1 and 6. Preliminary data suggest an engagement rate of about 20-30% in the BAC/CRC group. Assuming a steady loss to attrition that yields 80% completers, and a within-subject correlation of 0.3, the methods of Diggle et al. (Diggle, Heagerty et al. 2002) show that our sample size of 125 in each group yields 80% power for differences of about 15% in engagement rates between the two groups (e.g., 80% power for BAC/CRC: 25% vs. Mobile: 40%, corresponding to a RR=1.6 and an OR=2.0)

**Propensity score model to account for non-randomized allocation:** The participants are not randomly assigned to the mobile rapid induction intervention and BAC/CRC groups, so it is possible that there will be confounding of the group effect with the effects of characteristics of the participants. We will use a propensity score approach (Rosenbaum 2002, Rothman, Greenland et al. 2008) to account for this. We will use a broad range of baseline variables as covariates in a logistic regression model predicting treatment group, including age, race/ethnicity, gender, number of previous overdoses, number of previous treatments for opiate use disorder, type of opioid used, and depression. The model will yield predicted probabilities of BAC/CRC group for all participants (the propensity score), and we will create a five-level ordinal variable based on the quintiles of the propensity score. We will then include this ordinal variable as a stratum variable in our models.

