**Analyses for the primary aim:** i.e. to evaluate the impact of the mobile, transitional MAT intervention on its ability to engage participants in targeted, existing MAT treatment slots at 1- and 6-month post-enrollment. For each of the 1- and 6-month time points, we will classify participants as being engaged/not-engaged (where non-engaged will include dropped out or missing). We will compare the groups on engagement rates at the two time points using a repeated measures logistic regression model, incorporating the propensity score as described above (Diggle, Heagerty et al. 2002). The fixed effects will be binary indicators of treatment group and time point; we will test for a group by time interaction to assess whether the group effect differs at month 1 and month 6. As there are only two time points, we will use an unstructured covariance matrix to accommodate within-participant covariance.

**Analyses for Aim 2:** We will also use a repeated measures model to compare the groups on the ASI drug composite score at months 1 and 6. The model will be similar to that described for the engagement analyses of Aim 1, but with a beta distribution assumed for the response, to accommodate the bounded range (zero to one) of the ASI composite scores. We will compare the groups on the number of overdoses per patient using repeated measures Poisson regression models, if there is sufficient variability in the number of overdoses reported. If a low rate of overdoses causes convergence issues for the Poisson model, we will classify participants as having no overdoses versus at least one, and compare the groups using repeated measures logistic regression models.

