**Missing data.** For the longitudinal analyses described above, premature discontinuation from treatment and occasional missing daily use indicators will lead to incomplete data. The repeated measures models described above can make use of all available data provided by subjects, but the inferences drawn from them will be unaffected by the missing data only if the missing data can be regarded as ignorable, essentially meaning that missingness can be predicted/explained from the baseline data and from responses obtained prior to drop-out. We will assess the sensitivity of our main analyses to the presence of missing data by performing a sensitivity analysis, in which we will obtain estimates of the group effect under various non-ignorability assumptions. We will use selection models to examine the effects of missing data (Robins, Rotnitzky et al. 1995), in which we will explicitly model the probability of premature discontinuation at a time point as a function of baseline characteristics and responses at previous time points, using logistic regression models, and incorporate the predicted probabilities into a weighted analysis of the main hypotheses.

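### The beta model planned for the ASI drug composite cannot use scores of exactly 0 or 1, and the plan gives no rule for them

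*Combined protocol and SAP*

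**What the plan says.** Section 3.8.2 makes this a secondary endpoint: "Evaluate the impact on the number of overdose and evaluate the change in substance use and severity of addiction", using the ASI drug composite at months 1 and 6. Section 3.7 has the ASI drug and alcohol section administered at baseline and at both follow-ups.

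The Aim 2 paragraph of section 5 (printed under 5.2) carries over the Aim 1 model, "with a beta distribution assumed for the response, to accommodate the bounded range (zero to one) of the ASI composite scores". The plan therefore gives the range as running from zero to one, and chooses the beta distribution for that reason.

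No boundary rule appears in the study summary, the ASI description in 3.7, section 3.8.2, the Aim 2 paragraph or the missing-data paragraph. None of them mentions an inflated model, a transformation or an alternative model. The only fallback in the Aim 2 paragraph is for the overdose count, whose Poisson model is used "if there is sufficient variability in the number of overdoses reported".

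**The concern.** The beta distribution is a usual choice for a bounded score, but it covers only the open interval. An analyst who follows the text and meets a zero must stop, discard the observation, alter it or change the model, and the plan chooses none of these.

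Zeros are plausible at follow-up. The mobile service is modelled on the STEP programme (section 3.3), of which section 3.1 reports: "More than 90% of those who remained in treatment at 12 months were opiate-abstinent". The power case in 5.2 assumes 25% engaged under usual care and 40% in the mobile arm. If low severity goes with engagement, zeros may be more frequent in one arm.

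Discarding a zero also creates a missing value because of the value itself. The missing-data paragraph says the repeated measures inference is safe only when missingness can be explained by baseline data and earlier responses, and this kind cannot. The comparison would then describe non-zero scores only, and any group difference in the share at zero would be lost.

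**Working it through.** **1. Plan's own figures.** There is no power statement for Aim 2. The Aim 1 statement reproduces: effective n per arm = 125 × 0.80 / [(1 + 0.3)/2] = 153.8, and 25% vs 40% at two-sided 5% gives 80.5% against the stated 80%. It is used here only as the source of the 25% and 40% rates.

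**2. Likelihood at the boundary.** The beta log-density contains (a − 1) log y + (b − 1) log(1 − y). With (a, b) = (2, 6) it is minus infinity at y = 0 and at y = 1. With (0.5, 6) it is plus infinity at 0 and minus infinity at 1. Neither end can enter a fit. One standard implementation (statsmodels) stops with an error when zeros are present.

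**3. Leaving out zeros, with zeros linked to engagement.** Assume that only engaged participants score zero and that a share s of them do, so zeros are z0 = 0.25s (usual care) and z1 = 0.40s (mobile). Assume non-zero means m0 = 0.22 and m1 = 0.18. The values of s, m0 and m1 are assumptions; the documents give none.

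Share of the mean difference kept = (m0 − m1) / [(1 − z0)m0 − (1 − z1)m1].

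| s | zeros, usual care vs mobile | difference, all scores | share kept | power, beta on non-zero scores | power, fractional logit on all scores |
|---|---|---|---|---|---|
| 0.1 | 2.5% vs 4% | 0.2145 − 0.1728 = 0.0417 | 0.04/0.0417 = 96% | 92% | 87% |
| 0.25 | 6.25% vs 10% | 0.20625 − 0.162 = 0.04425 | 90% | 87% | 87% |
| 0.5 | 12.5% vs 20% | 0.1925 − 0.144 = 0.0485 | 82% | 85% | 90% |
| 0.9 | 22.5% vs 36% | 0.1705 − 0.1152 = 0.0553 | 72% | 81% | 97% |

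Power is from 400 simulated data sets (Monte Carlo error roughly 1 to 2 points): 125 per arm, two visits, correlation 0.3, beta precision 8 (assumed), and the follow-up of section 3.7, "We anticipate follow-up rates of 95% and 90% at Month 1 and 6, respectively".

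**4. Other patterns, same means** (log-odds, mobile minus usual care).
- Non-zero scores alone: logit(0.18) − logit(0.22) = −1.516 + 1.266 = −0.25.
- Zeros 10% in each arm: all-score means 0.198 and 0.162, logit difference −1.643 + 1.399 = −0.24, so essentially no bias on this scale. Power in 300 data sets was 86% for beta on non-zero scores and 67% for fractional logit on all scores.
- Zeros 20% vs 10%: all-score means 0.176 and 0.162, logit difference −1.643 + 1.544 = −0.10 (about −0.09 in simulation). Leaving out zeros still gives −0.25, an overstatement.

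**5. Replacing zeros by a constant, then fitting beta.**
- Zeros 10% each (all-scores effect −0.24): 0.01 gives about −0.20 with power about 60%; 0.0001 gives about −0.15 with power about 23%.
- Zeros 6.25% vs 10% (all-scores effect −0.29), constants 0.01, 0.001, 0.0001, 0.00001: estimates −0.28, −0.30, −0.32, −0.33; power 91%, 82%, 72%, 64% (300 data sets).

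**6. Difference lying wholly in the zeros.** A separate illustration used 100 per arm, one visit, a non-zero mean of 0.20 in both arms and zeros of 10% vs 25%, so the true mean difference is −0.20 × 0.15 = −0.030. Leaving out zeros gave +0.001, the adjustment (y(N − 1) + 0.5)/N gave −0.051, a floor of 0.001 gave −0.055 and a floor of 0.000001 gave −0.070.

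**The case against.** The best defence is that the documents do not predict any zeros. The STEP figure concerns opiate abstinence at 12 months among people still in treatment. Aim 2 uses a composite over drugs, at months 1 and 6, in everyone. That defence stands as to size: the figure shows that zeros are plausible, not how many there will be. The means and precision in the working are also assumed.

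A second defence is that one sentence fixing a boundary adjustment in advance would close the gap. It would remove a choice made after seeing the data. It would not remove the dependence on an arbitrary constant shown in step 5.

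A reader might infer four stronger things that are not supported.
- *That the planned model loses power.* In general it does not. With few or equal zeros, the beta model on non-zero scores has equal or higher power (92% vs 87%, 87% vs 87%, 86% vs 67%), although it then tests non-zero scores only.
- *That the bias always favours no difference.* Its direction depends on which arm has more zeros.
- *That a participant with a zero is lost altogether.* Only the zero visit is lost; a non-zero score at the other visit stays in.
- *That the overdose comparison is materially compromised.* Section 3.7 plans to "compare the two groups with respect to the rate of continued opioid use and subsequent overdoses", and no section says whether confirmed fatal overdoses count. City figures suggest few: 1,217 × 0.88 = 1,071 deaths a year; divided by 120,000 or 70,000 users, times 250 × 0.5 years, this is about 1.1 to 1.9. Participants all overdosed in the past year, so this may be low. If two deaths fell in one arm and 10% to 20% of each arm had a non-fatal overdose (assumed), a risk ratio of 1.00 would become 1.16 or 1.08 (14.5/12.5 or 27/25), well inside its 95% interval (0.48–2.10 or 0.61–1.64). This is a detail to clarify.

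**Conclusion.** The specification gap is certain: the plan names a model that cannot take values inside the range it states, and offers no alternative. Its consequence is unknown in size and direction because the share of zeros is not documented. Under the assumed means, leaving out zeros keeps between 96% and 72% of the mean difference when zeros follow engagement, makes almost no difference on the log-odds scale when zeros are equal, and overstates the effect when usual care has more of them. Substituting a constant moves both the estimate and the power with the constant.

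This should be corrected before the data are analysed. It concerns a secondary endpoint and does not touch the Aim 1 analysis or its power.

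**What to change.** In the Aim 2 paragraph, replace the beta model with a fractional-logit repeated measures model (GEE with robust standard errors). Keep the planned group, time, group-by-time and propensity-stratum terms, and state that all ASI drug composite scores, including 0 and 1, are analysed as observed with no replacement value. A zero-and-one-inflated beta model is an acceptable alternative if the overall mean difference is named in advance as the Aim 2 test.

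Keep the planned weighting, which is to "incorporate the predicted probabilities into a weighted analysis of the main hypotheses", as a sensitivity analysis, and apply it to this endpoint as well. As a minor clarification, add a sentence saying whether confirmed fatal overdoses count in the Aim 2 overdose number.

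The cost is wording; no new data are needed. There are two downsides. First, an unweighted GEE needs a stronger missing-data assumption than a likelihood model. In a deliberately adverse simulation (600 data sets, zeros 12.5% vs 20%, month-6 dropout driven by the month-1 score in opposite directions by arm, about 76% retained), the month-6 effect was −0.27 unweighted and −0.35 weighted, against −0.35 without dropout. The weighted analysis should therefore be reported beside the main one. Second, if zeros are equally common in the arms, using all scores has less power than using non-zero scores alone.

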#### 6.2 Adverse Events

Adverse events that occur at any point in the trial will be identified, managed, and documented in accordance with reporting requirements of the the City IRB (the IRB of record) and the sponsor (the CDC). Adverse events are defined as negative biologic events and/or social harms that occur during the course of the trial. When needed, referrals to medical treatment or specialists will be made. All patients will have comprehensive psychiatric and medical screening prior to randomization and at each counseling and assessment where evaluations for AEs will be routine. A member of the research team will be available at all times to answer questions and assess possible AEs. Participants will be withdrawn from the study if they show severe deterioration or if determined clinically necessary for other reasons.

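### The Aim 2 overdose model compares counts without time at risk, so interview timing that differs between the two groups would shift the rate ratio

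*Combined protocol and SAP*

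**What the plan says.** Overdose is an Aim 2 outcome (section 3.4) and a secondary endpoint (section 3.8.2). Under Analyses for Aim 2 in section 5.2 the plan states: "We will compare the groups on the number of overdoses per patient using repeated measures Poisson regression models". If low counts stop that model converging, participants are split into any versus no overdose and compared by repeated measures logistic regression. The Aim 1 model, which the Aim 2 paragraph follows, has indicators for group and time point. No offset, person-time, recall period, data source or rule for death is given for the overdose outcome in that paragraph, in the missing-data paragraph, in section 3.8.2 or in the section 1 summary.

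On timing, section 3.7 says: "All assessments will be completed by trained research staff (not clinicians) at baseline, and again at 1- and 6-month post-enrollment". Section 4.9.1 gives the comparison group the same assessments at the same points. The mobile team's research assistants assess one group; assistants from the second subcontractor enrol and follow the other (sections 3.3 and 4.9.1). Section 3.5.1 explains why there is no randomisation.

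On adverse events, section 6.2 says that participants will be screened "at each counseling and assessment where evaluations for AEs will be routine". Scheduled study counseling is described only for the mobile group, and only for the one-month intervention.

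**The concern.** A Poisson model without an offset estimates a ratio of mean counts. That equals a ratio of rates only if the groups have the same time at risk. The time indicator removes the planned difference between a 1-month and a 5-month window, but not differences in each participant's actual interval. An interview held late, a month-1 interview missed and then recalled over a longer window, or follow-up cut short all change the interval.

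These could differ by group. Allocation is not random, different staff trace each group, and the mobile group has frequent contact in month 1, which may make its members easier to find. The propensity score uses baseline variables and cannot correct follow-up timing. If usual-care participants are reached later, the mobile intervention looks protective with no true effect; if their windows are more often truncated, it looks harmful.

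A second question is where the count comes from. The plan refers only to overdoses being reported. If events learned at mobile-team contacts entered the count, the mobile group would have an extra source in month 1.

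**Working it through.** **The plan's own figure.** The only power statement concerns engagement: "80% power for BAC/CRC: 25% vs. Mobile: 40%, corresponding to a RR=1.6 and an OR=2.0", with "Assuming a steady loss to attrition that yields 80% completers, and a within-subject correlation of 0.3". For two proportions, two-sided 5%, 80% power, no continuity correction:

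n = [1.960·√(2·0.325·0.675) + 0.842·√(0.25·0.75 + 0.40·0.60)]² / 0.15² = 152.

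Two time points with correlation 0.3 give a factor (1 + 0.3)/2 = 0.65, so 152 × 0.65 = 98.8. Dividing by 0.8 gives 123.5, or 124 per group against 125 stated. The figure reproduces but says nothing about overdoses.

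**Inputs for overdoses**
- From the documents: 125 per group (section 5.2); planned windows of 1 and 5 months (section 3.7). The 5% level is stated only for the primary hypothesis ("We will test this hypothesis at a 5% level of significance"); I assume two-sided 5% here.
- Assumed: 1 to 2 overdoses per 12 months, i.e. 1/12 = 0.083 to 2/12 = 0.167 per month, anchored on the entry criterion of an overdose in the past 12 months. The documents give no rate.
- Assumed: gamma frailty with shape 1, and every difference in timing between groups.

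**Expected rate ratio (RR) without an offset, true RR = 1.** A participant observed for t months has expected count λt. With both rows present, the group term estimates the ratio of mean total time at risk, mobile over usual care.
- Month-6 interview late by a mean of 0.25 versus 1 month: (1 + 5.25)/(1 + 6) = 6.25/7 = 0.893.
- Month-6 window truncated (uniform from 0.05 to 5 months, mean 2.525) in 10% versus 20%: mobile 0.9·5 + 0.1·2.525 = 4.7525, usual care 0.8·5 + 0.2·2.525 = 4.505; 5.7525/5.505 = 1.045.
- The same in 5% versus 35%: 5.87625/5.13375 = 1.145.
- Month-1 interview missed in 5% versus 20%, recall since the last interview: month-6 window ratio 5.05/5.20 = 0.971.

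**Simulation.** Group and time terms, cluster-robust errors, 1,500 runs per scenario (Monte Carlo error about 1.1 points). Ranges cover the two overdose rates.

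| Mobile vs usual care | RR, no offset | Rejection | RR, log-time offset | Rejection |
|---|---|---|---|---|
| Windows as planned | 1.00 | 4.9–5.1% | not run | not run |
| Month-6 row missing at random, 10% vs 20% | 1.00–1.01 | 5.0–5.1% | not run | not run |
| Month 1 missed, 5% vs 20% | 0.97–0.99 | 5.3–6.2% | 1.00 | 5.3–6.3% |
| Truncated, 10% vs 20% | 1.04 | 6.7% | 1.00–1.01 | 5.2–5.5% |
| Truncated, 5% vs 35% | 1.15–1.16 | 9.3–12.3% | 1.00 | 4.4–4.8% |
| Late by mean 0.25 vs 1 month | 0.89–0.90 | 9.5–10.3% | 1.00 | 4.5–6.1% |

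A repeat of the last row with 8,000 runs gave RR 0.89 at both rates, with rejection 8.7% and 10.8%. With the offset, RR was 1.00 and rejection 5.2% and 5.7%.

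**Detection, if it occurred.** Suppose interviews capture a share s of overdoses and the mobile group's month 1 is captured in full. The six-month RR is (1 + 5s)/(6s): 5.5/5.4 = 1.02 at s = 0.9, 4.5/4.2 = 1.07 at 0.7, and 3.5/3.0 = 1.17 at 0.5. An offset does not change this (simulated 1.01–1.03, 1.07 and 1.17).

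**Fallback.** Under a constant rate, P(any overdose) = 1 − exp(−λt), so log(−log(1 − P)) = log λ + log t. A complementary log-log link therefore takes the same offset; a logit link does not.

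**The case against.** The strongest reply is that the schedule is identical in both groups, so nothing in the plan itself produces unequal windows, and this is a secondary endpoint. That stands. Section 3.7 anticipates follow-up without distinguishing groups ("We anticipate follow-up rates of 95% and 90% at Month 1 and 6, respectively"), and modest differences barely move the result.

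Three stronger readings are tempting, and the documents do not support them.

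- *Detection bias is built into the design.* No section says adverse-event records feed the overdose count. Section 3.7 sets the overdose comparison within the interview plan, and both groups have the same interviews. Scheduled mobile contacts cover about one of six months, and section 6.2 also offers adverse-event assessment on demand without limiting it to one group. The number of contacts is not firm either: the section 4.7 footnote sets 3 per week for the whole team (12 in four weeks), while adding the peer and nurse visits in section 4.9.1 gives 4 per week (16). Extra capture would also raise the mobile count, hiding a benefit.
- *The false-positive rate reaches 12% to 33%.* This needs a full one-month average delay in one group, the month-6 window alone (RR 5/6 = 0.83), pure Poisson variance, and 0.05 to 0.20 overdoses per month. Counting both windows gives RR 6/7 = 0.86 and 10.7% to 28.3%; frailty of shape 1 lowers that to 9% to 15%. Nothing in the documents predicts such a delay.
- *Week 24 in the payment table (section 10.3) against month 6 elsewhere biases the comparison.* The table applies to all participants, and the time term absorbs a common shift.

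I make no claim that visit windows are absent: the schedule table in section 4.7 did not survive in the text available.

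**Conclusion.** The concern holds in a limited form. The overdose model and its fallback omit time at risk, and the outcome has no stated source or recall period. There is no bias if interviews run to schedule in both groups. Bias arises only if lateness, missed interviews or truncation differ by group, which non-random allocation and separate tracing teams make possible but do not establish.

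In the late-interview scenario the null rate ratio falls to about 0.89–0.90 and the false-positive rate is about 10%. Truncation in 5% versus 35% gives 1.15–1.16 and 9% to 12%. The smaller differences tested leave the false-positive rate below 7%. All of this rests on assumed overdose rates, an assumed frailty and assumed timing gaps, and the propensity strata were not modelled. An offset restores a ratio of about 1.00 and rejection of 4.4% to 6.3% in every unequal-window scenario in the table.

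Unequal detection is an open route, not a demonstrated bias; it has to be closed by defining the source, because an offset cannot correct it.

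**What to change.** In section 5.2, Analyses for Aim 2, add:

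> Overdoses will be counted from the same interview item in both groups at months 1 and 6, with recall since the last completed assessment, plus fatal overdoses from a death-record search applied identically to both groups. Events learned only through mobile-team contacts will not enter the count. The Poisson model will include log(days from the previous completed assessment to the current assessment or death) as an offset. The binary fallback will use a complementary log-log link with the same offset.

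The parts belong together. An offset based on the interval between assessments is right only if recall covers that interval; with a fixed look-back it would itself introduce bias. Running exposure to death while counting only interview reports would give a fatal overdose person-time and no event, hence the death search.

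The cost is small. Section 5.1 describes a database that can track visits, so intervals should be obtainable. The recall wording must be fixed on the form. Section 4.8.2 ties the National Death Index search to 90 days without contact; a wider trigger would need the consent wording checked. The offset assumes a roughly constant rate within each window, and non-fatal overdoses between a participant's last interview and death stay unobserved. If intervals prove equal, the offset should leave the group comparison essentially unchanged.
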